#### **8.4.1.2 Primary endpoint, OS**

OS is defined as the time from the date of randomization until death due to any cause. Any patient not known to have died at the time of analysis will be censored based on the last recorded date on which the patient was known to be alive.

Note: Survival calls will be made following the date of data cutoff for the analysis (these contacts should generally occur within 7 days of the data cutoff). If patients are confirmed to be alive or if the death date is post the data cutoff date, these patients will be censored at the date of data cutoff. Death dates may be found by checking publicly available death registries.

#### **8.4.1.3 Secondary endpoints**

##### ***Objective response rate***

ORR (per RECIST 1.1 as assessed by the Investigator) is defined as the number (%) of patients with at least 1 visit response of CR or PR. Data obtained up until progression, or the last evaluable assessment in the absence of progression, will be included in the assessment of ORR. Patients who go off treatment without progression, receive a subsequent therapy, and then respond will not be included as responders in the ORR.

##### ***Duration of response***

DoR (per RECIST 1.1 as assessed by the Investigator) will be defined as the time from the date of first documented response until the first date of documented progression or death in the absence of disease progression (ie, date of PFS event or censoring – date of first response +1). The end of response should coincide with the date of progression or death from any cause used for the RECIST 1.1 PFS endpoint.

DoR will not be defined for those patients who do not have documented response.

##### ***Disease control rate***

DCR (per RECIST 1.1 as assessed by the Investigator) is defined as the rate of best objective response of either CR, PR, or SD according to RECIST 1.1.

DCR-16w is defined as the percentage of patients who have a best objective response of CR or PR or who have SD for at least 16 weeks (-7 days), following the start of study treatment. DCR-24w is defined as the percentage of patients who have a best objective response of CR or PR or who have SD for at least 24 weeks (-7days), following the start of treatment.

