### **Tumor assessments**

Tumor assessments, based on RECIST 1.1, will be performed every 8 weeks ( $\pm 1$  week) for the first 48 weeks relative to the date of randomization and then every 12 weeks ( $\pm 1$  week) thereafter until RECIST 1.1-defined radiological progression is confirmed by a follow-up scan, if clinically feasible, as per Confirmation of Radiological Progression criteria ([Appendix B](#)). Patients who continue treatment beyond radiological progression should continue with tumor assessments on their regular imaging schedule for the duration of their treatment.

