- Obtain tumor sample. This may be an archived tumor sample (taken  $\leq 3$  years) or a fresh tumor biopsy if archived tissue is not available. Patients must be able to undergo a fresh tumor biopsy during screening or to provide an available tumor sample taken  $\leq 3$  years prior to screening. Tumor lesions used for fresh biopsies should not be TLs, unless there are no other lesions suitable for biopsy. Fine needle aspirate specimens are not acceptable. Note: tumor biopsy is optional for China cohort.
- Determine patient eligibility (see Sections 3.1 and 3.2)

At randomization, once the patient is confirmed to be eligible, the Investigator or suitably trained delegate will:

- Record the presence or absence of macro-vascular invasion as a stratification factor in the IWRS (yes versus no).
- Record the etiology of liver disease (Confirmed HBV versus confirmed HCV versus others) as a stratification factor in the IWRS.
- Record performance status (ECOG 0 versus 1) as a stratification factor in the IWRS.
- Obtain a unique randomization number via the IWRS. Numbers will start at **PPD** and will be **PPD** by IWRS as patients are eligible for entry into the study. The system will randomize the eligible patient to 1 of the treatment arms.

If the patient is ineligible and not randomized, the IWRS should be contacted to terminate the patient in the system.

Patients will begin treatment on Day 1. Treatment should start no more than 3 working days after being randomized. Patients must not be randomized and treated unless all eligibility criteria have been met.

If a patient withdraws from participation in the study, then his or her enrollment/randomization code cannot be reused. Withdrawn patients will not be replaced.

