**Table 2 Schedule of assessments for all immunotherapy arms treatment period**

	Screening	Treatment period					Final visit	Source
Durvalumab cycle	Week -4 to -1	C1	C2	C3	C4	C5 to PD a	At time of confirmed PD	
Day	-28 to -1	1						
Window (days)	NA	(+3 days, tumor assessments)	( $\pm 3$ days, tumor assessments and e-PRO assessments $\pm 7$ days)					
Archived tumor sample (optional)	X							5.5.1
Fresh tumor biopsy (optional)							X t	5.5.1
Tumor and disease assessments								
Disease assessment by RECIST 1.1 (CT or MRI) u	X	Q8W $\pm$ 1 week for the first 48 weeks (relative to the date of randomization) and then Q12W $\pm$ 1 week thereafter until RECIST 1.1-defined radiological progression followed by a subsequent scan if clinically feasible. The schedule of Q8W $\pm$ 1 week for first 48 weeks and then Q12W $\pm$ 1 week thereafter MUST be followed regardless of any delays in dosing.						5.1

a Visits continue every 4 weeks.

b Informed consent of study procedures and tumor biopsy sample may be obtained prior to the 28-day screening window, if necessary. If laboratory, imaging, or pathology procedures were performed for alternate reasons prior to signing consent, these can be used for screening purposes with consent of the patient. However, all screening laboratory and imaging results must have been obtained within 28 days of randomization. Note: tumor biopsy is optional for China cohort.

c For the first infusion, BP and pulse will be collected from patients prior to the beginning of the infusion (measured once from approximately 30 minutes before up to 0 minutes), at 30 minutes during the infusion (halfway through infusion), and the end of the infusion (approximately 60 minutes  $\pm$  5 minutes). These collection times should be followed for each of the durvalumab and the tremelimumab infusions. For subsequent infusions, BP and pulse should be collected during and post-infusion as per institution standard and as clinically indicated.

d Any clinically significant abnormalities detected require triplicate ECG results.

e If screening laboratory assessments (including clinical chemistry, hematology, coagulation) are performed within 3 days prior to Day 1 (first infusion day), they do not need to be repeated at Day 1.

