### **5.1 Efficacy assessments**

This study will evaluate the primary endpoint of OS. Efficacy assessments of PFS, TTP, ORR, DCR, DCR-16w, DCR-24w and DoR will be derived (by AstraZeneca) according to RECIST 1.1.

For all patients, the RECIST tumor response data will be used to determine each patient's visit response according to RECIST version 1.1 ([Appendix B](#)). It will also be used to determine if, and when, a patient has progressed in accordance with RECIST 1.1 and their best objective response to study treatment. RECIST 1.1 assessments will be performed on images from CT (preferred) or MRI, each preferably with IV contrast of the chest, abdomen (including liver and adrenal glands), and pelvis. Pelvic imaging is recommended only when primary or metastatic disease in the pelvic region is likely. Additional anatomy should be imaged based on signs and symptoms of individual patients at baseline and follow-up.

Baseline radiological tumor assessments are to be performed no more than 28 days before the date of randomization and, ideally, as close as possible to randomization ([Table 2](#) and [Table 3](#)). Follow-up assessments will be performed Q8W ( $\pm$ 1 week) for the first 48 weeks following randomization, and then Q12W ( $\pm$ 1 week) thereafter until confirmed PD. The imaging schedule must be followed regardless of any delays in dosing.

If an unscheduled imaging assessment is performed and the patient has not progressed, every attempt should be made to perform the subsequent assessments as per the standard imaging schedule. If a patient discontinues treatment (and/or receives a subsequent anticancer therapy) after the initial assessment of progression, the patient should continue to be followed with scheduled imaging until confirmed objective disease progression.

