**CCI**

### 8.5 Methods for statistical analyses

The formal statistical analysis of OS (primary endpoint) will be performed for the following efficacy test hypotheses (alternative hypotheses):

- $H_1$ : Difference between durvalumab **CCI** mg plus tremelimumab **CCI** mg **CCI** (Arm C) and sorafenib **CCI** mg **CCI** (Arm D)
- $H_2$ : Durvalumab **CCI** mg monotherapy (Arm A) not inferior to sorafenib **CCI** mg **CCI** (Arm D) with noninferiority margin of 1.08
- $H_3$ : Difference between durvalumab **CCI** mg monotherapy (Arm A) and sorafenib **CCI** mg **CCI** (Arm D)

Efficacy data for Arm B: durvalumab **CCI** mg plus tremelimumab **CCI** mg **CCI** combination therapy arm (which was closed for enrollment with Amendment 4) will be summarized descriptively, but will not be formally analyzed.

Descriptive statistics will be used for all variables, as appropriate, and will be presented by treatment arm. Continuous variables will be summarized by the number of observations, mean, standard deviation, median, minimum, and maximum. Categorical variables will be

summarized by frequency counts and percentages for each category. Unless otherwise stated, percentages will be calculated out of the population total for the corresponding treatment arm.

Baseline will be the last assessment of the variable under consideration prior to the intake of the first dose of treatment, except for efficacy variables. For efficacy variables, baseline is defined as the last visit prior to randomization.

All data collected will be listed. Efficacy and PRO data will be summarized and analyzed based on the FAS (intent-to-treat [ITT] population). PK data will be summarized and analyzed based on the PK analysis set. Safety data will be summarized on the safety analysis set.

Results of all statistical analysis will be presented using a 95% confidence interval (CI) and 2-sided p-value, unless otherwise stated.

**Table 16** details which endpoints are to be analyzed, together with pre-planned sensitivity analyses indicating which analysis is regarded as primary for that endpoint.

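### DCR-16w and DCR-24w time stable disease from first dose, but scans, PFS and TTP run from randomization, so a permitted dosing lag can fail a patient scanned on schedule

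*Protocol*

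**What the plan says.** The definitions of both endpoints are in Protocol Section 8.4.1.3 under Disease control rate. Apart from responders, DCR-16w counts patients "who have SD for at least 16 weeks (-7 days), following the start of study treatment", and DCR-24w counts those "who have SD for at least 24 weeks (-7days), following the start of treatment". Both clocks start at treatment.

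The rest of the tumour-based efficacy plan is tied to randomization:

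- **Scan schedule.** The Synopsis (Tumor assessments) sets scans every 8 weeks, plus or minus 1 week, "for the first 48 weeks relative to the date of randomization". Table 2 has "for the first 48 weeks (relative to the date of randomization) and then Q12W" and Section 5.1 has "for the first 48 weeks following randomization, and then Q12W".
- **Dosing delays.** Section 5.1 adds: "The imaging schedule must be followed regardless of any delays in dosing".
- **Baseline.** Section 8.5: "For efficacy variables, baseline is defined as the last visit prior to randomization".
- **PFS and TTP.** Section 8.4.1.3 starts both at randomization.

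Section 3.3 allows a gap between the two origins: "Treatment should start no more than 3 working days after being randomized". Table 12 assigns DCR-16w and DCR-24w to the full analysis set, and Section 8.3.1 keeps randomized patients who never received study drug in that set. Section 8.5.3.4 summarizes both endpoints as counts and percentages per arm.

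**The concern.** The 7-day allowance in each definition looks designed to match the 1-week scan tolerance, so that a patient scanned at the early edge of the window can still qualify. That works only if both are counted from the same date. Here the threshold is counted from first dose and the scan from randomization, so each day of lag takes a day off the early part of the window. A patient scanned within protocol and still stable can then be scored as not controlled solely because of the days between randomization and first dose.

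A second consequence concerns the analysis set. A randomized patient who was never dosed and whose best response is stable disease has no start-of-treatment date. Read literally, the definition either excludes that patient from qualifying or gives no time origin.

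Two stated secondary endpoints are involved, and Section 8.5.6.2 also uses them for Arm C versus Arm D in the PD-L1 and etiology subgroups. The OS hypotheses are not touched.

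**Working it through.** **Inputs.** Thresholds from Section 8.4.1.3; scan interval and tolerance from the Synopsis, Table 2 and Section 5.1; maximum lag from Section 3.3.

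**1. Thresholds, in days from first dose.**
- DCR-16w: 16 × 7 − 7 = 105.
- DCR-24w: 24 × 7 − 7 = 161.

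**2. Compliant scan windows, in days from randomization.**
- Week 16: 112 ± 7 = days 105 to 119 (15 days).
- Week 24: 168 ± 7 = days 161 to 175 (15 days).

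The first day of each window equals the threshold, so there is no slack.

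**3. Permitted lag.** Three working days are 3 calendar days after randomization on Monday or Tuesday, and 5 after Wednesday, Thursday or Friday. This assumes no public holidays.

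**4. Shortfall.** With lag d, a scan on day x after randomization is x − d days after first dose. It falls short when x − d < 105 (or 161), that is on days 105 to 104 + d (or 161 to 160 + d). That is d of the 15 days. If one day is added to the duration, as the DoR formula in Section 8.4.1.3 does, it is d − 1 of 15 for d of at least 1.

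| Lag d (days) | 0 | 1 | 2 | 3 | 4 | 5 |
|---|---|---|---|---|---|---|
| Earliest week-16 scan, days from first dose | 105 | 104 | 103 | 102 | 101 | 100 |
| Earliest week-24 scan, days from first dose | 161 | 160 | 159 | 158 | 157 | 156 |
| Window days short, of 15 | 0 | 1 | 2 | 3 | 4 | 5 |
| Same, with one day added | 0 | 0 | 1 | 2 | 3 | 4 |

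At d = 5 only scans on days 105 to 109 or 161 to 165 can be affected. These are counts of calendar days, not proportions of patients.

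**5. Target-day scans.** At d = 5: 112 − 5 = 107 ≥ 105 and 168 − 5 = 163 ≥ 161. They pass at every permitted lag.

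**6. When stable disease ends.** The definition does not say, so both readings were checked.
- *Ends at the last stable scan.* The table applies directly to patients whose deciding scan falls on a short day.
- *Runs to the PFS event or censoring date, as DoR does.* Fewer patients are affected. One stable at week 16 who progresses at an in-window week-24 scan has at least 161 − 5 = 156 days and passes DCR-16w. A patient with earlier stable disease who progresses at an in-window week-16 scan counts as controlled on 15 − d of the 15 days: 15 down to 10, or 15 down to 11 with one day added. Classification still depends on the lag.

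**7. With randomization as origin.** The earliest compliant scans are at 105 and 161 days, which meet the thresholds, so 0 of 15 days fall short at any lag.

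**The case against.** The strongest reply is that the harm needs several things to coincide: a lag of at least one day (two if a day is added), a scan in the first few days of the window, that scan being the deciding date for stable disease, and no CR or PR. A later stable scan rescues a patient for DCR-16w, and Table 2 places randomization in the Cycle 1 Day 1 column, so same-day dosing, with no effect at all, is foreseen. The endpoints are descriptive, the protocol shows no difference in lag between arms, and redefining them after the final primary analysis planned for Q4 2021 has its own cost. All of this stands, and it limits the size of the point.

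It is also fair that the end of stable disease, the day-count convention and the handling of never-dosed patients could be settled in an analysis plan not seen here. The time origin is different, because the protocol itself fixes it at treatment start and nowhere reconciles it with the scan schedule.

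A further objection is that, if stable disease runs to the progression date, counting from randomization makes DCR-16w slightly more lenient towards patients who progress at the week-16 visit. That is true: 15 of 15 window days instead of 10 to 15. But the present text already counts most of those days, and which ones depends on the lag. The change removes that dependence without creating a new problem. The objection that the efficacy baseline is a reference assessment rather than a time origin is reasonable; the point rests on the scan schedule, PFS and TTP without it.

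**Conclusion.** The point holds. DCR-16w and DCR-24w run on a different clock from the scans that determine them and from PFS and TTP, and the 7-day allowance leaves no room for the dosing lag that the protocol permits. At most 5 of 15 compliant window days are affected at each visit (4 with one day added), assuming a lag of no more than 5 calendar days. The number of patients cannot be derived, because the protocol gives neither actual lags, nor scan dates, nor the share of patients whose classification rests on these visits. Responders and target-day scans are unaffected.

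This should be corrected, but it is a small defect in two descriptive secondary endpoints and does not bear on the OS conclusions.

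**What to change.** In both definitions in Section 8.4.1.3, replace the reference to the start of treatment with *following randomization*, and keep the thresholds at 105 and 161 days. Every compliant scan day then qualifies at any lag, and every patient in the full analysis set has a time origin.

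The cost is one phrase in each definition and one change to the derivation. Because Version 8.0 is later than the planned final primary analysis, document the change and, if results already exist under the current wording, report both versions. The change does not settle when stable disease ends; that remains to be stated separately.

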### ***Progression-free survival***

PFS (per RECIST 1.1 as assessed by the Investigator) will be defined as the time from the date of randomization until the date of objective disease progression or death (by any cause in the absence of progression) regardless of whether the patient withdraws from therapy or receives another anticancer therapy prior to progression. Patients who have not progressed or died at the time of analysis will be censored at the time of the latest date of assessment from their last evaluable RECIST 1.1 assessment. However, if the patient progresses or dies after 2 or more consecutive missed visits, the patient will be censored at the time of the latest evaluable RECIST 1.1 assessment prior to the 2 missed visits. If the patient has no evaluable visits or does not have baseline data, they will be censored at Day 1 unless they die within 2 visits of baseline, then they will be treated as an event with date of death as the event date.

The PFS time will always be derived based on scan/assessment dates and not visit dates.

RECIST 1.1 assessments/scans contributing toward a particular visit may be performed on different dates. The following rules will be applied:

- For Investigator assessments, the date of progression will be determined based on the earliest of the RECIST 1.1 assessment/scan dates of the component that indicates progression.
- When censoring a patient for PFS, the patient will be censored at the latest of the scan dates contributing to a particular overall visit assessment.

### ***Time to progression***

TTP (per RECIST 1.1 as assessed by the Investigator) is defined as the time from randomization until objective tumor progression; TTP does not include deaths. If patients died without progression, they will be censored at the time of death.

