### **3.10.2 Withdrawal of the informed consent**

Patients are free to withdraw from the study at any time (study drug[s] and assessments) without prejudice to further treatment.

Patients who withdraw consent for further participation in the study will not receive any further study drug(s) or further study observation, with the exception of follow-up for survival, which will continue until the end of the study unless the patient has expressly withdrawn their consent to survival follow-up. Note that the patient may be offered additional tests or tapering of treatment to withdraw safely.

A patient who withdraws consent will be asked about the reason(s) for withdrawal and the presence of any AE. The Investigator will follow-up AEs outside of the clinical study.

If a patient withdraws consent, they will be specifically asked if they are withdrawing consent to:

- All further participation in the study, including any further follow-up (eg, survival contact telephone calls)
- Use of their study generated data
- Use of any samples (see Section [5.5.6](#))

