### **Symptomatic deterioration**

Symptomatic (clinical) deterioration is not a descriptor of an objective response: it is a reason for stopping study therapy.

Patients with 'symptomatic deterioration' requiring discontinuation of treatment without objective radiological evidence of disease progression at that time should continue to undergo tumor assessments where clinically feasible.

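### TTP is censored at the date of death however long ago the last scan was, so unscanned time can count as progression-free; the PFS missed-visit rule should also govern TTP

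*Protocol*

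**What the plan says.** Section 8.4.1.3 defines TTP as time from randomization to objective tumor progression by Investigator RECIST 1.1 and adds "TTP does not include deaths". The only censoring rule is: "If patients died without progression, they will be censored at the time of death". It has no condition on when the patient was last scanned. Sections 8.5 (Table 16) and 8.5.3.2, which name the stratified log-rank test for A vs D, C vs D and C vs A, add none.

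The PFS definition, immediately before it in 8.4.1.3, is fuller. Patients without an event "will be censored at the time of the latest date of assessment from their last evaluable RECIST 1.1 assessment". It also says "if the patient progresses or dies after 2 or more consecutive missed visits, the patient will be censored", the censoring date being the latest evaluable assessment before the missed visits.

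The imaging schedule is in the Synopsis: "Tumor assessments, based on RECIST 1.1, will be performed every 8 weeks". That interval, with a window of one week either way, applies up to week 48 counted from randomization; later scans are 12 weeks apart.

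Two provisions let scanning end while the death date stays known. Under Section 3.10.2, patients who withdraw consent "will not receive any further study drug(s) or further study observation, with the exception of follow-up for survival", and Section 3.10.2.1 has sites re-check survival status of withdrawn and potentially lost patients, using death registries where available. Appendix B says that patients stopping treatment for symptomatic deterioration without radiological progression should continue "tumor assessments where clinically feasible".

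**The concern.** TTP events can be seen only on scans. Once scanning stops, a patient can no longer have an event, but the rule keeps anyone who later dies in the risk set until death. Those patients enlarge the denominator and lower the estimated progression hazard. The PFS paragraph guards against this and the TTP paragraph does not, so the same unscanned interval is handled in two ways for two endpoints built from the same scans.

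If scan drop-out were equal across arms, the main effect would be an optimistic TTP curve in every arm. The trial is open-label, with an oral control and infused experimental drugs, so drop-out from imaging could differ by arm. The arm with more drop-out would then look better on TTP.

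The mirror case is progression first seen after two or more missed visits. PFS censors it before the gap, whereas TTP as written counts an event at the late scan.

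**Working it through.** The protocol states no event count, power or median for TTP, so there is no planned figure to reproduce.

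**One patient under both rules.** Scans fall at weeks 8, 16, 24, 32, 40, 48, 60, 72 and so on. Suppose the last evaluable scan is at week 16 without progression, no scan follows, and death is at week 60.

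- PFS: the visits at weeks 24, 32, 40 and 48 were missed, so censoring is at week 16.
- TTP: censoring is at week 60.
- Unscanned time credited as progression-free: 60 − 16 = 44 weeks.

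The rules part once two visits have been missed: 2 × 8 = 16 weeks after the last scan on the 8-week schedule, 2 × 12 = 24 weeks on the 12-week schedule. If death comes sooner, PFS has an event and TTP is censored on the same date, which is the ordinary difference between the endpoints.

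**Illustration 1: true HR 1, continuous time, 40,000 patients per arm.** From the protocol: median OS 11.5 months (applied to both arms), 22 months of non-uniform accrual, cutoff at 37.5 months (Section 8.2). Assumed: median TTP 4 months; stated shares stop scanning at an exponential time with mean 2.5 months, independently of progression. The columns differ in where scan-stoppers who died are censored.

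| Stopping | Result | At death | At last scan |
|---|---|---|---|
| 10% Arm D, 5% experimental | HR | 1.040 | 0.997 |
| 20% Arm D, 10% experimental | HR | 1.082 | 0.994 |
| 10% both arms | median TTP, months | 4.17 | 3.97 |
| 20% both arms | median TTP, months | 4.44 | 4.02 |

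With equal stopping the median lengthens by 4.17 − 3.97 = 0.20 and 4.44 − 4.02 = 0.42 months.

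**Illustration 2: true HR 1, the protocol's scan schedule, 40,000 patients per arm.** From the protocol: median OS 16.5 (Arm C) and 11.5 months (Arm D), follow-up 15.5 to 37.5 months. Assumed: median TTP 3 or 5.5 months, stopping at a uniform time in weeks 0 to 32, living patients censored at the last scan. Each cell gives the results for median TTP 3 and 5.5 months.

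| Stopping, C / D | HR, TTP as written | HR, PFS-type rule |
|---|---|---|
| 0% / 0% | 0.991; 0.994 | 0.991; 0.994 |
| 20% / 20% | 1.018; 1.025 | 0.989; 0.993 |
| 10% / 30% | 1.183; 1.193 | 0.998; 1.000 |
| 30% / 10% | 0.881; 0.881 | 0.986; 0.990 |

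With 20% stopping in both arms, the six-month progression-free fraction in Arm D rises from 27.7% to 32.3% (median TTP 3 months) or from 50.0% to 53.5% (5.5 months). Under the PFS-type rule it stays within about half a percentage point of its no-stopping value. The Kaplan-Meier median, which can fall only on scan dates here, did not differ between the two rules in any scenario.

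Patients who actually die without progression after such a gap are fewer than those who stop: 2.5% to 3.5% of an arm at 10% stopping, 5.3% to 7.1% at 20%. Among them in Arm D, median time from last scan to death was about 47 weeks.

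**The case against.** **Effect and reach.** The affected group is narrow. Scans are to continue until confirmed progression despite stopping treatment or starting another therapy (Sections 3.9.1 and 5.1), so leaving treatment alone does not trigger the problem. The stopping rates are invented. With 2 × 385 = 770 patients and about 70% having events, there are about 540 events and the standard error of the log HR is about 2/√540 = 0.086. The shifts ln 1.04 = 0.039 and ln 1.08 = 0.077 are each below one standard error. No alpha is attached to TTP, and PFS, which has the gap rule, is reported for the same comparisons. All of this stands and limits the weight of the point.

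**Left to the SAP.** Detailed censoring rules often are. That covers what the TTP paragraph omits, but censoring at death is stated outright, and a gap rule in the SAP would have to override it.

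**Imperfect remedy.** Scan stopping after symptomatic deterioration is not independent of progression. When stoppers were made to leave in the second half of their time to progression, with shared frailty, death-date censoring gave HR 1.09 (10% against 5%) and 1.17 (20% against 10%). Last-scan censoring still gave 1.05 and 1.12. The bias shrinks but remains.

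**Stronger readings the text does not support.** A reader might infer that the rule credits unscanned time to patients who died but not to those still alive. The TTP paragraph does not say where living patients are censored, so that contrast cannot be established. A reader might infer a bias favoring the experimental arms. The direction depends on which arm loses more scans, and with more stopping in Arm D the experimental arm looks worse. Nor do TTP and PFS strictly contradict each other: they are different endpoints, each rule can be followed, and the fault is an inconsistent convention.

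**Conclusion.** The point holds as a modest but avoidable flaw in a named secondary endpoint. As written, TTP counts unscanned time as progression-free for patients who die without documented progression after missing two or more assessments in a row, while PFS censors the same patients before the gap. That follows from the text alone.

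The size does not. It rests on assumed stopping rates and TTP medians: a null HR of about 1.04 to 1.08 at 10% against 5% and 20% against 10% stopping, and 1.18 to 1.19 or 0.88 only under a 30% against 10% imbalance. With equal stopping the HR stays close to 1 (1.02 to 1.03 at 20%), and the distortion is mainly in the curve. OS, H1 to H3 and the sample size are untouched.

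**What to change.** In the TTP paragraph of Section 8.4.1.3:

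1. Where death or progression follows two or more missed assessments in a row, censor TTP at the latest evaluable RECIST 1.1 assessment before the gap, as for PFS.
2. Leave deaths without such a gap censored at death. Moving every death without progression to the last scan would go further than the PFS rule does.
3. State that living, progression-free patients are censored at their last evaluable assessment, as for PFS.

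The cost is a short text change, reusing a derivation the PFS analysis already needs. Median TTP may come out slightly shorter. Because stopping linked to progression still leaves some bias, the TTP report should not present the rule as a full correction.
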